#### 8.2.4 Cytokines and Inflammatory Markers

Cytokines and inflammatory markers include the following parameters: Immunoglobulin (Ig) E, IgG, IgM, C-reactive protein (CRP), Erythrocyte sedimentation rate (ESR), interferon  $\alpha$  (IFN-  $\alpha$ ), IFN- $\beta$ , Chemokines (Macrophage inflammatory protein (MIP)-1a and membrane cofactor protein (MCP)-1), Granulocyte-macrophage colony stimulating factor (GM-CSF), interleukin (IL)-1 $\alpha$ , IL-1 $\beta$ , IL-6, IL-8, IL-12, and Tumor necrosis factor –  $\alpha$  (TNF-  $\alpha$ ). Cytokines and inflammatory markers will be analyzed in the same way as the vital signs using the evaluable set.

### 8.2.5 TEGSEDI Administration and Exposure

TEGSEDI administration will be summarized using the safety set by both individual study visit and an overall study drug administration using a derived algorithm. Each visit will summarize the injection location, dose (mg), volume, number of patients having any hypersensitivity and

 	
Title: Statistical Analysis Plan
 
Program Name: "A Phase 4 Safety Study Assessing the Adverse Events Occurring Within 24 Hours of TEGSEDI Administration in Patients with polyneuropathy of Hereditary Transthyretin-mediated Amyloidosis (hATTR-PN)"
 
Protocol #: TEG4004
 
[REDACTED]
 
Version: Final 2.0 Effective Date: 06 October 2023

--	---

the number of patients taking any preventive measures prior to administration as recorded on the Dosing at Visit eCRF. For the overall analysis, the first on-site visit injection will initiate the start of TEGSEDI for this protocol. It will be assumed that the dose at a specific visit will be applied weekly from each specific visit until the subsequent visit, unless captured in the injection dosing log. Total exposure will be estimated using the number of doses, duration of exposure and dose intensity as mg/week and will use both the visit date as recorded for the on-site injection in combination with the dosing log form to calculate any changes.

#### 8.2.6 Concomitant Medications

Concomitant medications will be coded using the most recent World Health Organization Drug Dictionary Version and will be updated on re-runs on an ongoing basis. Concomitant medications will be summarized using the safety set by therapeutic/pharmacological subgroup (ATC level 3) and preferred term (ATC Level 5). Concomitant medications given as a preventive measure will be summarized by therapeutic/pharmacological subgroup, preferred term, by treatment month and overall.

#### 8.2.7 Procedures

Procedures will be listed but not summarized.

#### 8.2.8 Anti-drug Antibody (ADA) Data

The hypersensitivity reactions will be summarized by ADA status (Yes/No).

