### 9.2.2.1.2. Initial Treatment Visit (Month 0) and Every 4 Months Including End of Study Visit

**Pre-injection assessments** will be performed prior to administration of each dose of TEGSEDI at study visits. Pre-injection assessments will include:

- Abbreviated Physical examination, i.e. weight and vital signs, general appearance, dermatological, respiratory, cardiovascular and abdomen. (except Month 0 if they were performed at Screening)
- Concomitant Medications
- Laboratory testing
  - IgE, IgG, IgM (see [Annex 1](#))
  - Inflammatory markers: C-reactive protein (CRP), Erythrocyte sedimentation rate (ESR), interferon  $\alpha$  (IFN-  $\alpha$ ), IFN- $\beta$ , Chemokines (Macrophage inflammatory protein (MIP)-1a and membrane cofactor protein (MCP)-1), Granulocyte-macrophage colony stimulating factor (GM-CSF), interleukin (IL)-1 $\alpha$ , IL-1 $\beta$ , IL-6, IL-8, IL-12. Tumor necrosis factor –  $\alpha$  (TNF-  $\alpha$ ) (see [Annex 1](#))
  - ADA sampling at Month 0 visit pre-injection first dose and at End of Study visit, pre-injection
  - Urine pregnancy testing for women of childbearing potential
  - Additional blood samples will be drawn and stored for possible future non-genetic testing in this study.
- Adverse events since last study visit

**Post injection assessments** will be made at 1 hour  $\pm$  15 minutes; 2 hour  $\pm$  15 minutes; 4 hour  $\pm$  30 minutes; 8 hour  $\pm$  30 minutes and 20-30 hours following injection of TEGSEDI. Post-injection assessments will include:

- Vital signs
- Laboratory testing
  - IgE, IgG, IgM (see [Annex 1](#))
  - Inflammatory markers: CRP, ESR, IFN- $\alpha$ , IFN- $\beta$ , Chemokines (MIP-1a and MCP-1), GM-CSF, IL-1 $\alpha$ , IL-1 $\beta$ , IL-6, IL-8, IL-12, TNF-  $\alpha$  (see [Annex 1](#))
  - Additional blood samples will be drawn and stored for possible future non-genetic testing in this study
- Adverse events post injection at study visit
- The ADA sample is only drawn post injection, at the 20-30 hour time point, in the event of a hypersensitivity reaction

In addition to these study visits, the patient will be monitored according to the applicable product label.

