#### ***9.2.3.2. Laboratory Assessments***

Laboratory analyte samples will be collected and processed throughout the study at the central laboratory. ESR will be processed at the local laboratory. During their study visit, IgE, IgG, IgM, and inflammatory marker testing will occur at the time points noted in [Table 1](#) and [Table 2](#).

Samples for ADA will be taken at the Month 0 visit prior to TEGSEDI injection and at the last visit in all patients. If the patient experiences a hypersensitivity reaction within 24 hours of any dose of TEGSEDI administration during a study visit, the patient will have a further ADA test at the 20-30 hour time point and at their Post-Treatment Follow-up visits for 12 months or when one of the Milestones for Study End is triggered, whichever is earliest. Additional blood samples will be drawn and stored for possible future non-genetic testing in this study. For example, future tests may measure biomarkers or other safety parameters. These blood samples will be stored during the study and destroyed upon completion of the final study report.

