## 6 Schedule of Assessments

The study will consist of a Screening/Qualification period, a Treatment period and Post-Treatment Follow-up period as per Table 1 and Table 2.

The Screening/Qualification period is defined as the interval of time from the signing of informed consent until the first on-study dose of TEGSEDI.

The treatment period begins at the time of the first on study TEGSEDI administration and the end of treatment period is defined as follows:

- For patients who complete treatment with TEGSEDI on study, the last observation in the treatment period will be the 20-30 hour post-injection visit of the last administered TEGSEDI dose on study. If the time of the last TEGSEDI dose is missing, or the time of the assessment in question is missing, the assessment will be included in the treatment period if it occurred on the same day or one day subsequent to the last dose of TEGSEDI
- For patients who discontinue TEGSEDI or withdraw from the study and continue with TEGSEDI outside the study, the early termination (ET) visit will serve as the end of the treatment period

For patients who discontinue TEGSEDI, the post treatment follow-up period begins after the end of the treatment period, as defined above, and ends with the last available data collected per the clinical trial protocol. Data for the post-treatment follow-up period will be analyzed and summarized separately for patients who develop a hypersensitivity reaction.

	Title: Statistical Analysis Plan				
	Program Name: "A Phase 4 Safety Study Assessing the Adverse Events Occurring Within 24 Hours of TEGSEDI Administration in Patients with polyneuropathy of Hereditary Transthyretin-mediated Amyloidosis (hATTR-PN)"				
	Protocol #: TEG4004				
	[REDACTED]				
	Version: Final 2.0 Effective Date: 06 October 2023				

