**Table 1. Schedule of Assessments for Patients Who do not Develop a Hypersensitivity Reaction**

Study Periods	Screening 	Treatment Period				Post-Treatment Follow-up (Patients who discontinued TEGSEDI) 8-weeks (+/- 1 week) 
		Initial Treatment Visit (Month 0) and Every 4 months Visit (+/- 2 weeks) for 12 months		End of Study Visit		
Procedures and Testing	-2 to 0 weeks prior to first study injection	Pre-injection	Post injection 1-hour ± 15 mins 2-hour ± 15 mins 4-hour ± 30 mins 8-hour ± 30 mins 20-30 hours	Pre-injection	Post injection 1-hour ± 15 mins 2-hour ± 15 mins 4-hour ± 30 mins 8-hour ± 30 mins 20-30 hours	Early Termination Visit 
Informed Consent	X					
Demographics	X					
Medical History	X					
Full Physical Examination 	X					
Abbreviated Physical Examination 		X 		X		X X
Height	X					
Weight	X	X 		X		X X
Vital Signs	X	X	X	X	X	X X
Urine Pregnancy Testing	X 	X 		X 		X 
IgE, IgG, IgM		X	X	X	X	X

	Title: Statistical Analysis Plan
	Program Name: "A Phase 4 Safety Study Assessing the Adverse Events Occurring Within 24 Hours of TEGSEDI Administration in Patients with polyneuropathy of Hereditary Transthyretin-mediated Amyloidosis (hATTR-PN)"
	Protocol #: TEG4004
	[REDACTED]
	Version: Final 2.0 Effective Date: 06 October 2023

Inflammatory Markers		X	X	X	X	X	
Samples for Possible Future Testing		X	X	X	X	X	X
ADA		X 		X		X 	
Adverse Events Post Injection at Study Visit			X		X		
Concomitant Medications	X	X		X		X	X

1. The Screening visit and the Month 0 visit can occur on the same day.
2. The Physical Examination and Weight does not need to be completed at the Month 0 study visit if they were performed during Screening.
3. If the patient withdraws from the study, the patient should return for an ET visit within 2 weeks after the decision to withdraw from the study. If the patient discontinues TEGSEDI, they should have an ET visit within 2 weeks of the decision to end treatment and one follow-up visit 8-weeks ( $\pm$  1 week) after their last dose of TEGSEDI. If the ET and the 8 week follow up visit are within 2 weeks of each other, the assessments can be combined.
4. Urine pregnancy testing is only for women of childbearing potential as defined in the protocol.
5. The baseline ADA sample is only drawn at the Month 0 visit.

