**Table 2. Schedule of Assessments for Patients Who Develop a Hypersensitivity Reaction**

	Title: Statistical Analysis Plan				
	Program Name: "A Phase 4 Safety Study Assessing the Adverse Events Occurring Within 24 Hours of TEGSEDI Administration in Patients with polyneuropathy of Hereditary Transthyretin-mediated Amyloidosis (hATTR-PN)"				
	Protocol #: TEG4004				
	Version: Final 2.0 Effective Date: 06 October 2023				

Study Periods	Screening 	Treatment Period			Post-Treatment Follow-up (Patients who discontinued TEGSEDI) 8-weeks (+/- 1 week) 4-month (+/- 2 weeks) 8-month  (+/- 2 weeks) 12-month  (+/- 2 weeks) Post-Treatment visits
		Initial Treatment Visit (Month 0) and Every 4 months Visit (+/- 2 weeks)		Early Termination Visit	
Procedures and Testing	-2 to 0 weeks prior to first study injection	Pre-injection	Post injection 1-hour ± 15 mins 2-hour ± 15 mins 4-hour ± 30 mins 8-hour ± 30 mins 20-30 hours		
Informed Consent	X				
Demographics	X				
Medical History	X				
Full Physical Examination 	X				
Abbreviated Physical Examination 		X 		X	X
Height	X				
Weight	X	X 		X	X
Vital Signs	X	X	X	X	X
Urine Pregnancy Testing	X 	X 		X 	
IgE, IgG, IgM		X	X	X	
Inflammatory Markers		X	X	X	

	Title: Statistical Analysis Plan
	Program Name: "A Phase 4 Safety Study Assessing the Adverse Events Occurring Within 24 Hours of TEGSEDI Administration in Patients with polyneuropathy of Hereditary Transthyretin-mediated Amyloidosis (hATTR-PN)"
	Protocol #: TEG4004
	[REDACTED]
	Version: Final 2.0 Effective Date: 06 October 2023

Samples for Possible Future Testing		X	X	X	X
ADA		X 	X 	X	X 
Adverse Events Post Injection at Study Visit			X		
Concomitant Medications	X	X		X	X

1. The Screening visit and the Month 0 visit can occur on the same day.
2. The Physical Examination and Weight does not need to be completed at the Month 0 study visit if they were performed during Screening.
3. The 8 month and 12 month follow-up visits will occur only if a Milestone for Study End has not been triggered.
4. Urine pregnancy testing is only for women of childbearing potential as defined in the protocol.
5. The baseline ADA sample is only drawn at the Month 0 visit. The ADA sample is only drawn post injection, at the 20-30 hour time point, in the event of a hypersensitivity reaction.

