## Identification of Risk Factors for AEs

For AEs observed within the 24 hour drug administration window, patient's medical history, baseline characteristics and concomitant medications will be reviewed and potential risk factors will be explored.

In addition, the impact of ADA formation on development of hypersensitivity reactions will be evaluated by summarizing the hypersensitivity reactions by ADA status.

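### Must the SAP define ADA status, and add same-visit ADA samples, before it summarises hypersensitivity reactions by that status?

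*Combined protocol and SAP*

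**What the plan says.** SAP 8.2.8 reads "The hypersensitivity reactions will be summarized by ADA status (Yes/No" and stops there. Under Identification of Risk Factors for AEs, SAP 8.2.2.2 gives the purpose: "the impact of ADA formation on development of hypersensitivity reactions will be evaluated by summarizing the hypersensitivity reactions by ADA status".

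The samples behind this are set out in several places:

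- Protocol 9.2.2.1.2 schedules "ADA sampling at Month 0 visit pre-injection first dose and at End of Study visit, pre-injection".
- SAP Table 1, footnote 5: "The baseline ADA sample is only drawn at the Month 0 visit".
- SAP Table 2, footnote 5: "The ADA sample is only drawn post injection, at the 20-30 hour time point, in the event of a hypersensitivity reaction".
- SAP Table 2 adds samples at early termination and at the post-treatment follow-up visits for patients who react. SAP 6 handles the follow-up data apart: "Data for the post-treatment follow-up period will be analyzed and summarized separately for patients who develop a hypersensitivity reaction".
- Other blood is drawn and stored before and after the injection at each study visit, with no assay assigned. Protocol 9.2.3.2 says of it: "These blood samples will be stored during the study and destroyed upon completion of the final study report".

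SAP 8 states that the analyses are descriptive, with no hypothesis tests.

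**The concern.** A yes/no status has to come from some sample, and there are several candidates: Month 0, the 20-30 hour sample, the last sample, or any positive. These need not agree. SAP 5.1 admits patients already on TEGSEDI with no cap on earlier doses, so a positive Month 0 result may be pre-existing antibody or antibody formed on drug.

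The schedule raises a second doubt. To say that antibody formation leads to reactions, one wants antibody status before the reaction, and the same measurement in patients who did not react. At Months 4 and 8 the plan has neither. Reactors are also sampled more often, which under some definitions would make them look positive more often.

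Risk factors are part of the study objective, and this is the only ADA summary that the SAP describes. A reader could therefore take it as evidence, for or against, that antibodies cause the reactions.

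**Working it through.** **The plan's own figure.** The only design calculation is in protocol 9.4: 75 patients give a 95% chance of seeing an event with a 4% rate. Check: 1 − 0.96^75 = 0.953. It reproduces, and the ADA summary does not depend on it.

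**ADA samples by study dose.** Sources are protocol 9.2.2.1.2 and SAP Tables 1 and 2, taking Month 12 as the End of Study visit.

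| Dose | Reactor, pre-dose | Reactor, 20-30 h | Non-reactor, same visit |
|---|---|---|---|
| Month 0 | yes | yes | yes, pre-dose |
| Month 4 | no | yes | none |
| Month 8 | no | yes | none |
| End of Study | yes | yes | yes, pre-dose |

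Two of the four doses have a pre-dose sample in everyone. If Month 12 is not the last visit (protocol v2.0, section 9.1.1, allows up to 24 months), then Months 12, 16 and 20 are in the same position as Months 4 and 8 unless one of them is the final visit.

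**Age of the last earlier sample.** Weeks = months × 365.25 / 12 / 7.

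- Month 4: 17.4 weeks, or 15.4 to 19.4 with the ±2 week visit window.
- Month 8: 34.8 weeks, or 32.8 to 36.8.

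SAP 8.2.5 assumes that "the dose at a specific visit will be applied weekly from each specific visit until the subsequent visit", so these are about 17 and 35 doses.

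**Number of samples.** By SAP Table 1 a non-reactor has 2 (Month 0, and End of Study or early termination). Protocol v2.0, section 9.2.2.1.4, could be read as giving some who stop treatment a third. By SAP Table 2 a reactor who stops treatment has 3 in the treatment period (Month 0, 20-30 h, early termination), and up to 7 if the four follow-up visits counted.

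**Could this distort the table?** The documents give no positivity rate and no status rule, so both are assumed here.

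1. *Any positive counts, 20% of samples positive, no true effect, independent samples.* P(any positive in n) = 1 − 0.8^n, which is 36.0% for 2 samples and 48.8% for 3. Odds ratio = (0.488/0.512) / (0.360/0.640) = 1.69. Serial samples from one patient are correlated. A beta-binomial model with intraclass correlation 0.8 gives 23.2% and 24.9%, odds ratio 1.10. At 0.95 it gives 20.8% and 21.2%, odds ratio 1.02.
2. *One later sample per patient, steady accrual to 30% by month 12, no true effect.* The monthly hazard is −ln(0.7)/12 = 0.0297. By month 4 the proportion positive is 1 − exp(−4 × 0.0297) = 11.2%. A reactor sampled at month 4 against a non-reactor sampled at month 12 gives (0.112/0.888) / (0.30/0.70) = 0.29.

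The two assumed rules push in opposite directions, and the plan states neither.

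**Scale.** If 4% of 75 patients reacted (an assumption that borrows the design rate), that is 3 patients. With so few, sample dates and results can be read patient by patient.

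**The case for a change.** The case for a change is that the objective names risk factors, that a status rule chosen after the data are seen can colour the table, and that the word impact promises more than the samples hold. The stored blood also offers a time-limited way out: pre-injection samples from Months 4 and 8 exist in all patients until the final report is complete. Protocol v2.0 adds a further gap. Section 9.2.3.2 ties the extra ADA sample to reactions after doses given at a study visit, whereas section 9.2.2.1.5 covers reactions at any time in the study. Reactions to doses taken between visits may therefore have no 20-30 hour sample.

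The description of the gap stands. The remedies do not clearly improve on the plan:

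- Setting a reactor's 20-30 hour sample against a non-reactor's End of Study sample builds in the unequal timing that gave 0.29 above. It also leaves between-visit reactors without a sample.
- Month 0 status is properly ordered in time and can be tabulated from the plan as it is. In patients starting at Month 0, however, it precedes any antibody formed on drug.
- Assaying stored blood is extra laboratory work. The documents do not say whether those samples suit the ADA assay. Two visits in 75 patients would be 150 assays, but enrolment is at least 75, so that is not an upper limit.

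The missing definition may also not be missing. The SAP implements protocol v3.0 and lists mock tables among its appendices, and the protocol's amendment log records that ADA and its rationale were added to Annex 1. None of these was available, and a status rule often sits in table shells.

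**Conclusion.** No change to the plan is called for. What remains is an unwritten definition for one descriptive, untested summary, together with a purpose phrased more strongly than the samples allow. Analysts can close the first in a table footnote that names the sample used, shows Month 0 status separately and reports missing ADA as missing. SAP 6 already directs that follow-up data from reactors be summarised separately. The second is a matter of reading: the table shows association.

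The limit that stays is specific. From the scheduled ADA samples, antibody formation cannot be timed against reactions at the Month 4 and Month 8 doses, where the last earlier sample is about 17 and 35 weeks old. It can be examined at Month 0 and End of Study. The size of any distortion is unknown: the odds ratios of 0.29 and 1.02 to 1.69 rest on assumed rules and rates and disagree in direction, so they do not show that the plan gives a wrong result. The conclusion assumes that Month 12 is the End of Study visit and that the unseen documents do not prescribe a harmful rule.

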### 9 Annual Progress Reports

No formal interim analysis is planned. Data related to disposition, exposure and safety considerations will be reported on an annual basis. Specifically, the following information will be presented separately in table format as described below.

- Recruitment status
- Subject disposition
- Demographics and Baseline Characteristics
- Exposure
- Number of Patients with Any Treatment-emergent Adverse Events occurring within 24 hours of TEGSEDI Administration by Study Visit
- Treatment-emergent Adverse Events occurring within 24 hours of TEGSEDI Administration by System Organ Class, Preferred Term and Study Visit

 	
Title: Statistical Analysis Plan
 
Program Name: "A Phase 4 Safety Study Assessing the Adverse Events Occurring Within 24 Hours of TEGSEDI Administration in Patients with polyneuropathy of Hereditary Transthyretin-mediated Amyloidosis (hATTR-PN)"
 
Protocol #: TEG4004
 
[REDACTED]
 
Version: Final 2.0 Effective Date: 06 October 2023

--	---

- Treatment-emergent Adverse Events Related to TEGSEDI by System Organ Class, and Preferred Term
- Treatment-emergent Serious Adverse Events by System Organ Class, and Preferred Term
- Treatment-emergent Adverse Events of Special Interest by System Organ Class, and Preferred Term
- Listing of Pregnancies

## 10 Appendices

Appendix A – TEG4004 Annual Progress Report Template

Appendix B – Mock TLFs
